### Presentation of Results

- Estimates of rates and 95% CIs were available for BinomialCL.
- Risk difference and 95% CI are available from diff.
- Chi-square P values are available from PVALUE1.

### 8.2.3.2. Model Specifications of Sensitivity Analysis

#### Statistical analysis of binary categorical variables

#### Endpoints and parameters

- Endpoint: hematoma recurrence (trepanation/drainage group) or symptomatic hematoma progression (non-surgical group) rate of hematoma at 90 days after randomization
- Parameters:
  - OR and 95% CI

#### Input Variables

- AVAL: response variable
- TRTAN: groups
- SITEID: subject site number
- COUNT: number of subjects per level per group
- COVARIATES: adjustment Variables

#### SAS Code Sample

#### Generalized Linear Mixed-effects Model Example Code:

```
proc glimmix data=adeff descending;
  class site trtan;
  model aval/ count = trtan covariates / solution;
  random intercept / subject=site;
  ods output oddsratio= odds ratio estimates;
```

run;
Presentation of Results
• The OR and 95% CI for the ratio can be obtained from Odds Ratio Estimates.

### 8.3. Subgroup Analyses

The primary efficacy endpoint will be analyzed in the following subgroups:

- Age group(<70 vs  $\geq 70$ )
- Sex (male vs female)
- Surgical treatment strata (trepanation/drainage vs. no trepanation/drainage)
- Smoking status(yes vs no)
- Medical history of brain trauma (yes vs no)
- Any usage of antiplatelet or anticoagulant therapy before randomization(yes vs no)
- Any usage of statins within one month before randomization(yes vs no)
- Midline shift of baseline CT (<10 mm vs  $\geq 10$  mm)
- Hematoma thickness of baseline CT (<10 mm vs  $\geq 10$  mm)
- Hematoma volume of baseline CT (<Q3 of combined hematoma volume data,  $\geq Q3$  of combined hematoma volume data)
- Bilateral SDH (yes vs no)
- Embolized branches of MMA (main trunk only, distal only, main trunk & distal)

Subgroup analysis will use the same statistical analysis methods as described in Section 8.2.2.

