5.3 MMA Embolization

Participants allocated to the MMA embolization group will undergo cerebrovascular angiography followed by ipsilateral MMA embolization to address the SDH. Anesthesia, either general or monitored local, will be administered as per the procedural needs. The use of intravenous heparin during the procedure will be meticulously documented. Initially, femoral or radial artery access is established, followed by digital subtraction angiography (DSA) using a standard 5 French diagnostic catheter for cerebrovascular evaluation. Subsequently, a guiding catheter is positioned in the proximal external carotid artery, and a microcatheter is advanced into the main trunk of the MMA under roadmap guidance. Superselective angiography of the MMA is then performed to identify any hazardous collateral vessels, such as ophthalmic and petrous branches, prior to embolization. Absence of dangerous collaterals allows for embolization using ONYX-18 (Medtronic, USA) under blank fluoroscopic roadmap. Successful embolization is achieved when both frontal and parietal branches or the main trunk of MMA are selectively occluded. For comprehensive embolization, it is advised that the microcatheter navigates distally within the frontal and parietal branches, facilitating maximum penetration of embolic materials into the smaller vessels. In this trial, MMA embolization is

recommended to precede burr-hole drainage in patients assigned to the combined treatment group.

6. Study Process

This clinical study focuses on assessing the effectiveness of Middle Meningeal Artery (MMA) embolization in treating Chronic Subdural Hematoma (CSDH). It includes a detailed flowchart for the study process (Appendix 1), encompassing informed consent, enrollment, and various stages of evaluation. Key aspects involve obtaining written informed consent, medical history recording, vital signs monitoring, and a stringent randomization process using SAS software. The study also emphasizes comprehensive clinical examinations and evaluations, including routine blood tests, imaging (CT/MRI), and scoring assessments (mRS, EQ-5D) at multiple stages. Additionally, the study records hospitalization details, re-hospitalization rates, and surgery-related complications to ascertain the treatment's effectiveness and safety.

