7.3.3 Sub-Group analysis

In the evaluation of both primary and secondary outcomes, pre-specified subgroup analyses were conducted, focusing on distinctions between patients undergoing burr-hole drainage and those receiving optimal medical management. For safety assessments, the analysis encompasses all patients who were randomized and subsequently underwent the study

treatment.

8. Data Management

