Appendix 1. Study Flowchart

Study procedure	Screening period ^a	Baseline	Follow-up period			
			V0	V1	V2	V3
Visit time ^b	Day -14 to Day 0	Day 0		Discharge	Day 30	Day 90
Informed consent	X					
Demographic data	X					
Inclusion/exclusion criteria		X				
Medical history and previous medication	X					
Vital signs	X			X	X	X
Admission examination ^c	X					
CT/MRI ^d	X				X	X
DSA ^e		X				
Randomization and treatment		X				
Total hospitalization expenses			X		X	X
Efficacy endpoints					X	X
SAEs					X	
SDH-related death events					X	
Severe surgery-related complications					X	
Concomitant medication/treatment			X	X	X	X
mRS score	X				X	X
EQ-5D scale	X				X	X

^a Screening visit and baseline visit can be conducted on the same day

^b The visit time window is ± 7 days for V3, ± 14 days for V4, and ± 30 days for V5

^c Blood routine (red blood cell count, white blood cell count, platelet count, hemoglobin), coagulation (APTT, INR), hepatic and renal function (ALT, AST, BUN, Cr), electrolytes (potassium, sodium, chlorine), random blood glucose; urine HCG test is required for female of child-bearing potential

^d CT is mandatory and MRI is optional. The doctor should decide whether MRI is necessary based on the condition of the patient

^e This item is conducted only in MMA embolization group

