	
surgical treatment etc. The contraindications are: allergic to the drug used or having contraindications for the use of the drug.
 
Atorvastatin calcium and dexamethasone are recommended. Atorvastatin calcium with small dose and long course of treatment can be used in combination with dexamethasone. The specific treatment is subject to the local clinical diagnosis and treatment specifications or corresponding clinical guidelines, and is not specified in this study.
 
The application of hemostatic drugs will greatly increase the incidence risk of embolic diseases, so hemostatic drugs are not commonly used.
 
 
• Surgical Treatment: Surgical treatment in this study refers to trepanation and drainage, and local anesthesia + analgesia or general anesthesia can be used for trepanation and drainage.
 
 
Indications of trepanation and drainage: (1) There are clinical symptoms and signs of high intracranial pressure, with or without changes in consciousness and signs of cerebral hemisphere compression; (2) CT or MRI scan shows unilateral or bilateral subdural hematoma with thickness of > 10 mm, and midline shift of > 10 mm due to unilateral hematoma; (3) For those who have been treated with drugs for promoting hematoma absorption for 2 weeks or longer, and whose clinical manifestations and imaging examination have not improved significantly, or whose hematoma continues to increase or medication is intolerable, surgical treatment is recommended.
 
If the subjects in the embolization group need surgery, the embolization will be performed before trepanation and drainage.

Assignment	
 
• Eligible subjects will be randomized 1:1 to either conventional therapy (no MMA embolization) or MMA embolization.
 

Interim Analyses	
 
• The study includes two formal interim analyses, and efficacy analyses will be performed when approximately one-third and two-thirds of patients completed the 90-day follow-up.
 

Sample Size	
 
• 722 cases are expected to be enrolled in this study in China.
 

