### 8.2.2. Analysis Methods

- The primary analysis will compare groups using the CMH chi-square test (the stratification factor is whether or not to perform trepanation/drainage was performed), summarize the 90-day recurrence (trepanation/drainage group) / progression rate (non-surgical group) for the MMA embolization group and the control group using the two-sided 95% CI (Clopper-Pearson method) and summarize the two-sided 95% CI for the difference in recurrence or progression rates between the two groups using the Miettinen-Nurminen method.
- Sensitivity analyses will use generalized linear mixed-effects model to calculate ORs and their 95% CIs for the comparison of recurrence or progression rates between the two arms, with group as fixed effect, site as random effect. Results of multivariable analysis will also be

presented, including treatment group, sex, age, surgical treatment strata (trepanation/drainage vs. no trepanation/drainage), any usage of antiplatelet or anticoagulant therapy, hematoma volume of baseline CT as covariates.

Enter Analysis Methods and Results Presentation

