## 12. APPENDICES

### 12.1 Appendix 1: Treatment Period and Study Period

Treatment Period and Study Period						
Study Day						
Time points and assessment windows						
Study Flow Chart						
STUDY PROCEDURES	Screening a	Baseline	Follow-up Period			
Visit Time b	V0	V1	V2	V3	V4	V5
	-14 to Day 0	Day 0	At discharge	Day 30	Day 90	Day 360
Informed Consent	X					
Demographics	X					
Inclusion/Exclusion Criteria		X				
Medical History and Prior Medications	X					
Vital signs	X			X	X	X

Treatment Period and Study Period						
Admission examination c	X					
CT/MRI d	X				X	X
DSA e		X				
Randomized and treated		X				
Treatment and nursing costs			X		X	X
Efficacy Endpoints					X	X
Serious Adverse Events					X	
SDH-related death events					X	
Procedure-related serious complications					X	
Concomitant medication/treatment			X	X	X	X
MRS scale	X				X	X
EQ-5D Scale	X				X	X

A Screening visit and baseline visit may be on the same day

B V3 visit window is  $\pm 7$  days, V4 visit window is  $\pm 14$  days, and V5 visit window is  $\pm 30$  days

c Blood routine (red blood cell count, white blood cell count, platelet count, hemoglobin), coagulation function (APTT, INR), liver and kidney function (ALT, AST, BUN, Cr), Electrolytes (potassium, sodium, chloride, calcium), fasting blood glucose; Women of childbearing potential will need a negative urine HCG test to be enrolled. Those women of childbearing potential with positive or missing pregnancy test will not be included.

d CT is mandatory, MRI optional, and MRI examination may be performed at the physician's discretion according to the patient's condition

E Performed only in the MMA embolization group

Acceptable Time Windows for Follow-up Period

Treatment Period and Study Period	
Time Point	Acceptable Time Window
V3	±7 days
V4	±14 days
V5	±30 days

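### The embolized-branch subgroup in SAP 8.3 cannot take the between-arm comparisons of Section 8.2.2: controls treated as assigned fall in no level, and extent is settled after randomization

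*SAP*

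**What the plan says.** SAP Section 8.3 names twelve subgroups for the primary efficacy endpoint. The last is "Embolized branches of MMA (main trunk only, distal only, main trunk & distal"). The section closes with a rule that covers the whole list: "Subgroup analysis will use the same statistical analysis methods as described in Section 8.2.2".

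Section 8.2.2 is mainly a comparison of arms: "The primary analysis will compare groups using the CMH chi-square test", stratified by trepanation/drainage. It adds a Clopper-Pearson interval for the event rate in each arm, a Miettinen-Nurminen interval for the difference in rates, and a generalized linear mixed model that gives the odds ratio for treatment group.

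The SAP design overview defines the arms: "Eligible subjects will be randomized 1:1 to either conventional therapy (no MMA embolization) or MMA embolization". Protocol Section 5.3 places the procedure after allocation: "Participants allocated to the MMA embolization group will undergo cerebrovascular angiography followed by ipsilateral MMA embolization to address the SDH". Both visit schedules limit DSA to one arm (Protocol Appendix 1: "This item is conducted only in MMA embolization group"; SAP Appendix 1: "Performed only in the MMA embolization group").

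Protocol Section 7.3.3 foresees only one subgroup split, "focusing on distinctions between patients undergoing burr-hole drainage and those receiving optimal medical management".

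**The concern.** A subgroup analysis asks whether the effect of treatment against control differs across levels of a characteristic that both arms share. The other eleven items in Section 8.3 are patient history, baseline imaging, or the surgical stratum, which Protocol Sections 3.1 and 5 place before randomization. The embolized branches are different on two counts. They are a feature of the experimental treatment, so controls treated as assigned have no value. They also become known only once the procedure is done.

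An analyst who follows Section 8.3 literally cannot produce the between-arm results. The natural workaround, setting each extent against the whole control arm, would look like the other subgroup results but would lack their basis in randomization. At stake is the reading of which extent of embolization works better, a question of technique that this comparison cannot answer.

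**Working it through.** The plan gives no figure for this subgroup, so the check is mainly of which patients can enter each level and what each Section 8.2.2 output then needs.

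**1. Who can be placed in a level.** All three levels presuppose that an embolization was done. The control arm is defined by having none. Section 8.3 has no level for patients not embolized, and neither document gives a rule for assigning controls to levels. With controls treated as assigned, each level therefore has an empty control row.

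**2. What each Section 8.2.2 output does with an empty control row.** Within a branch level, for surgical stratum *h*, let *r1* and *r2* be the numbers in the embolization and control arms, *c1* and *c2* the numbers with and without an event, *N* the total, and *a* the events in the embolization arm.

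- *CMH test:* the statistic is [Σ(*a* − *r1·c1/N*)]² / Σ*V*, with *V* = *r1·r2·c1·c2* / [*N*²(*N* − 1)]. If *r2* = 0, then *r1* = *N* and *a* = *c1*, so the numerator is 0 and *V* = 0. With invented counts of 5 events in 100 and 4 in 64: *V* = 100·0·5·95/(100²·99) = 0 and 64·0·4·60/(64²·63) = 0. The statistic is 0/0.
- *Risk difference and Miettinen-Nurminen interval:* the control proportion is 0/0, so there is no difference to estimate.
- *Mixed-model odds ratio:* treatment group takes one value only, so its coefficient cannot be separated from the intercept.
- *Clopper-Pearson rate:* it needs one arm only, so it can be computed by extent within the embolization arm.

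**3. When and how the level is determined.** Protocol Section 5.3 has superselective angiography look for hazardous collaterals before embolization, makes embolization depend on their absence, counts either trunk occlusion or occlusion of both branches as success, and advises distal navigation of the microcatheter. Vessel anatomy and operator technique thus sort patients into levels after allocation.

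**4. The unstated alternative: each extent against all controls.** An illustration on assumed values that are not in the documents: no treatment effect, 12% risk in both arms, half the patients at 8% risk and half at 16%, and two equally sized levels with opposite 75/25 mixes.

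- Level A: 0.75·8% + 0.25·16% = 10%, so 10 − 12 = −2 points against control.
- Level B: 0.25·8% + 0.75·16% = 14%, so 14 − 12 = +2 points.
- With risks of 10%/14% the levels are 11% and 13% (±1 point). With 6%/18% they are 9% and 15% (±3 points).

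The levels average back to 12%, so the whole-arm comparison is unharmed. The planned difference is 12% − 5% = 7 points.

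**5. Scale.** The planned 722 reproduces. With pooled variance, two-sided 0.05 and 90% power, *n* = [1.960·√(2·0.085·0.915) + 1.282·√(0.12·0.88 + 0.05·0.95)]² / 0.07² ≈ 332 per arm, and 664/0.92 ≈ 722. If a level holds an assumed 10%, 20%, 33% or 50% of the 332 evaluable embolization patients, the expected events at 5% are about 1.7, 3.3, 5.5 and 8.3.

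**The case against.** The best defence is that the item never mentions controls. The between-arm reading comes only from the general closing sentence of Section 8.3, and Section 8.2.2 also includes per-arm Clopper-Pearson rates, which work here. On that view a descriptive display within the embolization arm may be all that was meant. The part about the rates stands: a reader might infer that nothing in the planned analysis can be computed, or that a comparison with all controls is the only way to carry it out, and neither is so. The rest does not stand, because the closing sentence makes no exception and the SAP nowhere limits this item to one arm.

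A reader might also infer that every level must contain zero controls. That holds only if no control is embolized. Under the ITT rule a control who crossed over stays in the control arm and could carry a value. Such a patient is still classified after randomization by a departure from assignment, so the wording must be conditional but the analysis is not rescued.

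Protocol Section 6.5 lists DSA among the examinations before randomization, which conflicts with the footnotes of both visit schedules; these passages must be reconciled. The conflict does not help here, since a diagnostic angiogram shows anatomy and not which branches were embolized.

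Finally, the consequence is limited. This is one of twelve subgroups, and an empty control row would show itself when the program is run. Both remarks are fair.

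**Conclusion.** The rule in SAP 8.3 does not work as written for this item. The CMH test, the Miettinen-Nurminen interval and the odds ratio cannot be validly produced by embolized extent; the Clopper-Pearson rates can, within the embolization arm. This rests on the definition of the control arm, on the absence of any rule that places controls in levels, and on the timing in Protocol Section 5.3.

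Two stronger readings should be resisted. One is that comparing each extent with all controls would forfeit randomization entirely. The control arm would remain an intact randomized group; the problem is selection within the embolization arm. The documents do not allow its size to be estimated, and the 1 to 3 points above depend wholly on assumed risks and mixes. The other is that a misleading claim will be published beside the baseline subgroups. The SAP does not describe the layout of the subgroup results, so this is a risk and not something planned.

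The primary comparison, its significance level and the sample size of 722 are unaffected. The point is worth correcting but of limited weight.

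**What to change.** Take the item out of the between-arm list in SAP 8.3, or keep it there and add a sentence that exempts it from the Section 8.2.2 comparisons.

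In its place, specify a table for the embolization arm only: number of patients, number of events, and event rate with exact 95% interval for each embolized extent. Add a category for patients allocated to embolization who were not embolized (for example, where angiography showed dangerous collaterals), so that the whole ITT arm is covered. Label the table descriptive and non-randomized, and give no between-arm p-value, risk difference or odds ratio.

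The cost is SAP wording and one table shell. Data collection, trial conduct, the primary analysis and the sample size do not change.

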7.1.3 Estimation of sample size

This study hypothesizes that MMA embolization may reduce the recurrence (operation group) or progression (conservative treatment group) of SDH. The estimated recurrence or progression rate of hematoma in the MMA embolization group is 5%, while that of control group is 12%. When estimating bilateral 5% for the statistical significance level, 90% for power, and 8% for an acceptable rate of loss to follow-up, the total sample size is estimated to be 722 cases.

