### **3. Sample Size Considerations**

The study hypothesizes that patients undergoing middle meningeal artery embolization may have lower symptomatic recurrence (in the trepanation/drainage group) and lower rates of symptomatic hematoma progression (in the non-surgical group) of subdural hematoma compared to patients who do not go MMA embolization. Two interim analyses will be conducted. With an expected symptomatic recurrence rate (trepanation/drainage group) / symptomatic progression rate (non-surgical group) after MMA embolization of 5% compared with 12% in the control group, and considering a loss to follow-up rate of 8%, a sample size of 722 cases with a two-sided alpha of 0.05 would yield 90% power.

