### 9.1.2.2. Statistical Analysis Methods

- 360 days recurrence or progression of SDH after randomization will be analyzed in the same way as the primary endpoint (Section8.2.2)
- Ordinal logistic regression will be used for intergroup comparison of mRS scale scores at 90 and 360 days after randomization, with treatment group, sex, age, surgical treatment strata (trepanation/drainage vs. no trepanation/drainage), any usage of antiplatelet or anticoagulant therapy within one month before randomization(yes vs no), hematoma volume of baseline CT as covariates.
- Other categorical secondary endpoints will be analyzed in the same way as the primary endpoint **(Error! Reference source not found.Error! Reference source not found.Section)**

- The linear mixed effects model approach will be used to estimate the mean estimate (95% CI) and the mean estimate (95% CI) of the differences between groups as well as the P values of the differences between groups for the change in maximum hematoma thickness at 90 days after randomization compared to baseline and the change in hematoma volume at 90 days after randomization compared to baseline; Treatment group variables, sex, age, surgical treatment strata (trepanation/drainage vs. no trepanation/drainage), any usage of antiplatelet or anticoagulant therapy within one month before randomization(yes vs no), hematoma volume of baseline CT , visit variables, and visit by treatment group variable interactions will be included in the model and site as the random effect.
- For other continuous secondary endpoints, T tests will be used to compare groups, and 95% confidence intervals for the difference in means between groups will be calculated using normal approximation.

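### SAP 8.3 plans no treatment-by-subgroup interaction test and no exploratory label, so discordant within-level p-values for the 11 baseline factors could be misread as effect modification

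*SAP*

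**What the plan says.** SAP 8.3 opens with "The primary efficacy endpoint will be analyzed in the following subgroups" and lists 12 factors. Eleven are baseline factors with two levels each. The twelfth, which MMA branches were embolized, has three levels. The section closes with its only statement of method: "Subgroup analysis will use the same statistical analysis methods as described in Section 8.2.2".

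SAP 8.2.2 contains:
- a test of treatment: "The primary analysis will compare groups using the CMH chi-square test", stratified by drainage or no drainage;
- Clopper-Pearson intervals for each arm's rate and a Miettinen-Nurminen interval for the risk difference;
- a mixed logistic model "with group as fixed effect, site as random effect", with a multivariable version that adds covariates as main effects.

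The sample code in SAP 8.2.3 likewise has no treatment-by-covariate term. The only interaction in the SAP is in 9.1.2.2, for hematoma thickness and volume: "visit variables, and visit by treatment group variable interactions will be included in the model". That one concerns visits, not subgroups.

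Protocol 7.3.3 plans a single factor. It says that "pre-specified subgroup analyses were conducted, focusing on distinctions between patients undergoing burr-hole drainage and those receiving optimal medical management".

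Neither document names a heterogeneity test of any kind, gives a multiplicity rule for subgroups, or says that subgroup results are exploratory.

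**The concern.** A two-arm method without a subgroup term can only be applied one level at a time. It yields an effect and a p-value for each level but no comparison between levels. Whether an effect differs between levels is a question about the difference of two effects. One p-value below 0.05 beside one above it does not answer that, because each level holds only part of the sample and its power is well below the trial's 90%.

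Protocol 7.3.3 sets out to look at distinctions between drained and medically managed patients, and the primary objective names both populations. A reader is therefore likely to ask whether embolization works in one and not in the other. The planned output cannot test that, and could suggest a difference where there is none.

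**Working it through.** **Inputs.** Event rates of 12% (control) and 5% (embolization), two-sided alpha 0.05, 90% power, 8% loss to follow-up, 1:1 allocation and N = 722 come from Protocol 7.1.3 and SAP 3. The split for baseline hematoma volume is about 75:25, because SAP 8.3 cuts it at the third quartile. Every other split is an assumption, taken here from 50:50 to 90:10.

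**Step 1: reproduce the plan's figure.** SAP 3 says "a sample size of 722 cases with a two-sided alpha of 0.05 would yield 90% power". With pooled rate 0.085,

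n per arm = [1.960 × √(2 × 0.085 × 0.915) + 1.2816 × √(0.12 × 0.88 + 0.05 × 0.95)]² / 0.07² = (0.773 + 0.501)² / 0.0049 = 331.5, so 332.

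Two arms give 664, and 664 / 0.92 = 721.7, so 722. The plan's figure is reproduced with 332 evaluable per arm.

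**Step 2: chance that exactly one level is significant when the effect is the same in both.** Let a and b be the powers in the two levels. The levels contain different patients, so

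P(exactly one significant) = a(1 − b) + b(1 − a).

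The powers below come from exact binomial enumeration of the two-sided two-proportion test, with 332 per arm divided between the levels and 12% vs 5% in each level.

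| Split | Power, larger level | Power, smaller level | Exactly one significant |
|---|---|---|---|
| 50:50 | 64% | 64% | 46% |
| 75:25 (volume cut) | 81% | 36% | 59% |
| 90:10 | 88% | 18% | 74% |

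The normal approximation gives 47%, 58% and 74%. With all 722 evaluable it gives 45%, 57% and 75%.

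**Step 3: dependence on the true effect, 50:50 split.** With equal powers the formula is 2a(1 − a).

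| True rates in both levels | Power per level | Exactly one significant |
|---|---|---|
| 12% vs 5% | 64% | 46% |
| 12% vs 8% | 23% | 36% |
| 12% vs 3% | 90% | 18% |
| 12% vs 12% | 5% | 10% |

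**Step 4: what an interaction test would do instead.** In 3,000 simulated trials per scenario (664 evaluable, 11 independent two-level factors, uniform 12% vs 5%), a Wald test of the log odds ratio interaction gave a false signal for about 3% to 4% of factors. The nominal rate is 5%. Over 11 independent tests the nominal chance of at least one false signal is 1 − 0.95¹¹ = 43%; the simulations gave 32% to 37%. An interaction test therefore removes most of the problem per factor, but it does not control error over the whole list.

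**Step 5: sparse levels.** A 25% level has 83 per arm and expects 83 × 0.12 ≈ 10 vs 83 × 0.05 ≈ 4 events. A 10% level has 33 per arm and expects about 4 vs 2. A Wald interaction test is unreliable with counts that small.

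**The case against.** The main objections, and what stands of each:

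- **The SAP does not say that tests will be run within each level, or that discordant p-values will be read as effect modification.** Both points are correct. Level-by-level repetition is the natural reading of 8.3 with 8.2.2, but it is an inference. A reader might infer that the trial plans to claim differences from within-level significance. The documents do not say so. The fault is that the plan supplies no valid comparison and no caution, not that it commits to an invalid claim.
- **SAP 8.2.2 already gives level-specific rates, risk differences, odds ratios and intervals.** True, and the fix keeps them. They still do not test a difference between levels.
- **The count of 12 overstates the problem.** This stands. Embolized branches are known only after treatment and have no counterpart in the control arm, so neither a randomized comparison within level nor an interaction test can be formed. The concern covers 11 factors.
- **The size is conditional.** This stands. A reader might infer that five or six false differences are to be expected over the 11 factors. At the design effect, 11 × 0.46 = 5.1 and 11 × 0.59 = 6.5, but that needs every split to lie between 50:50 and 75:25 and the true effect to equal the assumed one. The SAP fixes only one split. With all splits 50:50, the same sum at 12% vs 3% is 11 × 0.18 = 2.0.
- **The figures do not carry over to drainage versus conservative treatment.** This stands too. The two populations have different event definitions, 12% vs 5% is a single pooled assumption, and neither the split nor the stratum-specific rates are given.
- **The trial's main conclusion is unaffected.** Agreed: the tested hypothesis is the single pooled comparison.

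**Conclusion.** The concern holds for the 11 two-level baseline factors. The plan has no test of whether the treatment effect differs between levels, although Protocol 7.3.3 aims to examine exactly that for drained versus medically managed patients, and nothing marks subgroup results as exploratory.

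At the design effect, discordant significance under a uniform effect has a probability of about 46% to 74% per factor, depending on the split. The firmest of these figures is 59% for hematoma volume, where the SAP fixes the split. For a 50:50 factor the probability falls to 36%, 18% or 10% under the other effects examined. These results assume the same two rates in every level and 332 evaluable per arm; unequal baseline risk would change them. The importance of the drainage factor rests on the trial's objective, not on a computed figure. The primary result does not change. What is at stake is how it is interpreted across patient groups.

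**What to change.** Amend SAP 8.3 as follows:

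1. For each of the 11 baseline factors, test treatment-by-subgroup interaction in a logistic model with treatment, subgroup, their interaction and the drainage stratum. Omit the separate stratum term when the subgroup is itself the drainage stratum. Keep site as a random effect if the model is to match 8.2.2. Name an exact or penalized method for factors with sparse events.
2. Report the interaction p-value with level-specific effects and 95% confidence intervals, for example in a forest plot.
3. Label all subgroup results exploratory, without multiplicity control, and state that within-level p-values will not be used to claim differences between subgroups.
4. Take embolized branches out of the randomized subgroup comparisons and report them descriptively within the embolization arm.

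The cost is a few sentences of SAP text and light programming, with no new data and no change to the primary analysis. The drawback is that interaction tests have low power at this sample size, so most will be inconclusive. They should be written into the SAP before unblinding; added later, they would not be prespecified.
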